## STUDY PROTOCOL

### PURPOSE

We hypothesise that midodrine treatment of refractory hypotension in patients otherwise ready for discharge from the ICU shortens duration of receiving IV vasopressors and ICU length of stay without increasing hospital length of stay or putting the patient at risk of being readmitted to an ICU.

### SIGNIFICANCE AND BACKGROUND

Midodrine is an orally available alpha-1 agonist, which is currently FDA approved for the treatment of symptomatic orthostatic hypotension. This indication is generally reserved for patients with chronic orthostatic hypotension that significantly impairs their daily activities of living despite standard care because midodrine carries the risk of supine hypertension. However, in patients without orthostatic hypotension, this adverse reaction is theoretically less prevalent due to preserved baroreflex buffering that maintains blood pressure homeostasis. Midodrine has several unique pharmacological properties compared to other medications in its class: it exerts significantly less gastrointestinal effects, has minimal central nervous system side effects, and demonstrates excellent bioavailability following oral administration. These desirable pharmacological properties lead to midodrine's potential application for new indications.

One of the most frequently prescribed off-label indications for midodrine is prevention of intradialytic hypotension. A systematic review was conducted evaluating the use of midodrine for the prevention of intradialytic hypotension. 56 patients received a one-time dose of 2.5 to 10 mg of midodrine 15–30 minutes prior to each dialysis session compared to a placebo-control group. The midodrine group's mean pre- and post-dialysis systolic blood pressure (SBP) was 128.1 (90.5–138.7) mmHg and 115.5 (81.5–129.9) mmHg and pre- and post-dialysis diastolic blood pressure (DBP) was 72.4 (55.4–81.4) mmHg and 58.9 (50.2–72.5) mmHg. The control group's mean pre- and post-dialysis SBP was 123.2 (73–135.2) mmHg and 103.1 (64.9–116.5) mmHg and pre- and post-dialysis DBP was 58.1 (44–76.2) mmHg and 52.5 (32.6–66.8) mmHg. The midodrine group demonstrated a statistically significant greater post dialysis and nadir SBP with a mean difference of 12.4 mmHg (7.1–17.7;  $p < 0.0001$ ) and 13.3 mmHg (8.6–18;  $p < 0.0001$ ) and post dialysis and nadir DBP with a mean difference of 7.3 mmHg (3.7–10.9;  $p = 0.0001$ ) and 5.9 mmHg (2.7–9.1;  $p = 0.0004$ ) vs. the placebo control group.

Although frequently prescribed as an off-label indication, the optimal dosing range for midodrine in the treatment of hypotension unrelated to orthostasis has yet to be fully determined. Our proposed study will use the maximum dose that has been previously shown to have a strong correlation with effect on systolic blood pressure. This dosing is based on a recently published randomised, two-centre, double-blind, four-way complete crossover, single dose study in patients with neurogenic orthostatic hypotension. This study demonstrated that there was a linear relationship between dose and change in systolic blood pressure when administering a single dose of midodrine from 2.5 mg to 20 mg. These doses also produced a predictable blood pressure response and blood concentrations. The time to maximum concentration of midodrine was 15 to 30 minutes with an elimination half-life equal to 30 minutes, and active metabolite, dysglymidodrine, equal to 4 hours. There are limited efficacy and safety data supporting off-label use. Based on billing records, a total of 6,443 patients were prescribed midodrine as an inpatient at MGH since 1998. Utilisation of midodrine has steadily increased over the last decade with 1,200 patients being prescribed in 2010. Given that midodrine is only indicated to treat rare diseases, it is likely that the majority of these patients were prescribed midodrine as an off-label indication.

The only information available for off-label treatment of hypotension unrelated to orthostatic dysregulation is based on observational data. Midodrine was successfully used as an alternative to intravenous vasopressors in the treatment of hypotension related to carotid artery stenting. Eleven patients received intravenous dopamine infusion in an intensive care setting whereas 4 patients received midodrine in a regular telemetry floor to treat hypotension. The cost of hospitalisation was significantly higher in the dopamine group due to the need for ICU admission and no major side effects were noted in either group. In another study, midodrine was used as an alternative to intravenous inotropic therapy in patients with hypotension associated with stunned myocardium. The authors concluded that midodrine can shorten the duration of intensive care unit and hospital stay in this setting. At MGH's ICUs,

midodrine has been observed to effectively wean patients off continuous IV vasopressors. For patients whose only barrier to discharge from the ICU was administration of continuous medications, midodrine also appeared to decrease ICU length of stay. However, it is unknown if midodrine shortened their total hospital LOS or put the patient at risk of being readmitted back to an ICU. Additionally, midodrine appears to be well tolerated by patients when prescribed at MGH because there have been no safety reports submitted due to an adverse reaction.

No previous studies have examined the use of midodrine for the treatment of hypotension in an ICU setting. We are investigating a new indication for midodrine as the treatment for hypotension in critically ill patients. We expect that midodrine will decrease the time of patients being administered continuous vasopressors by 6 hours and therefore accelerate their readiness for ICU discharge. This has potential to have a significant impact on healthcare costs by reducing ICU and hospital LOS.

## DESCRIPTION OF RESEARCH PROTOCOL

### Study Design

The study is a randomised, double-blind, placebo-controlled, multi-centric trial expected to enrol 120 subjects in order to detect an expected statistically significant difference of 6 hours (from initiation of drug until discontinuation of IV vasopressors) between the two groups.

Subjects are being enrolled at:

1. Massachusetts General Hospital, Boston (MGH)
  - Local IRB: Partners Human Research Committee, protocol number: 2016P002045
2. Sir Charles Gairdner Hospital, Australia (SCGH)
  - Local IRB: Sir Charles Gairdner Hospital HREC, protocol Number: 2015-098
3. Beth Israel Deaconess Medical Center, Boston (BIDMC)
  - Local IRB: Committee on Clinical Investigations, protocol number: 2018P000162

### Recruitment

Subjects will be identified from the ICU census on a daily basis by study personnel and identified by other ICU clinicians. If identified subjects meet inclusion/exclusion criteria they will then be approached by a specialised health care provider. The specialised health care provider will be a physician that is part of the clinical staff in the ICU who has first-hand knowledge of the subject's medical history. This physician will approach potentially eligible subjects to introduce them to the research study. If both the specialised health care provider approves his or her subject to be contacted for research purposes and the subject agrees to be contacted by study staff discussed verbally during the course of providing medical care, a study physician will then approach the subject to obtain informed consent.

### Subject Selection

Inclusion criteria:

- At least 18 years of age
- Admitted to the intensive care services at MGH, SCGH, or BIDMC
- Requiring IV vasopressors at a rate of less than 100 mcg/min of phenylephrine, or 8 mcg/min of norepinephrine, or metaraminol 60mcg/min and unable to wean for more than 24 hours while still maintaining desired blood pressure goals.

Exclusion criteria:

- Clinical evidence of inadequate tissue oxygenation
- Clinical evidence of liver failure
- Hypovolemic shock or hypotension due to adrenal insufficiency (based on clinical suspicion or available routine testing)
- Pregnancy confirmed with a pregnancy test. Women between the ages of 18–55 who have not had a surgical hysterectomy will only be eligible for inclusion if they have a negative urine pregnancy test. Pregnancy testing will not need to be repeated if there is a documented negative urine pregnancy test that was obtained within 7 days prior to starting study drug, provided the woman was an ICU inpatient throughout that period of time.

- Chronic renal failure (serum creatinine >2mg/dL or 180 µmol/L)
- Severe organic heart disease (ejection fraction less than 30%)
- Acute urinary retention
- Pheochromocytoma (based on clinical suspicion)
- Thyrotoxicosis (based on clinical suspicion)
- Enrolment in another clinical trial
- Midodrine as pre-admission medication
- Any known allergies to midodrine
- Bradycardia (HR <50/min)
- No enteral route available

### Consent

Informed consent will be obtained from the participant by a study physician. If the subject lacks mental competency based on the mini mental status exam to provide informed consent, the subject's designated surrogate will be explained their responsibility as a LAR to make decisions on the patient's behalf, and will be asked to provide consent. The LAR will also be explained that should the participant re-gain mental capacity, he/she will be formally consented. As part of this, the study physician will address the patient explaining what procedures have been held so far, the purpose, risks and benefits of the study. The study physician will then explain the patient's right to decide as to whether they wish to continue being a participant in the study. Based on the patient's decision, study procedures will be continued or withheld immediately. The following categories of surrogates (listed in general order of preference) may provide consent in writing on behalf of potential subjects incapable of providing informed consent:

- Health Care Proxy, a court appointed guardian of the person with specific authority to consent to participation in the research study, but also next-of-kin in the following order of priority unless otherwise specified by law: spouse, adult child (18 years of age or older), parent, adult sibling (18 years of age or older), grandparent, or adult grandchild (18 years of age or older).

Assent of subjects is required for participation in the research unless the subject is incapable of giving assent due to his/her medical condition. If the individual objects to participation, s/he will not be enrolled. The Investigator will document the relationship of the surrogate to the subject in the research record.

### Study Procedures

Prior to randomisation, if subjects are eligible based on inclusion/exclusion criteria, informed consent will be obtained from participants. Once informed consent is obtained, the following information will be collected from the subject's medical record: demographics, past medical/surgical history, preadmission medication list, severity of illness at time of admission, blood pressure, aspartate aminotransferase, alanine aminotransferase creatinine, troponin, cortisol level.

The study drug or placebo will be selected based on the randomisation scheme and prepared by investigational pharmacists. All study personnel will be blinded, except the investigational pharmacist, to the treatment group of the subject. Subjects will be randomised to receive either 20 mg PO every 8 hours of midodrine, or placebo PO every 8 hours.

The study drug will be delivered in a double-blinded manner until:

- ICU discharge
- Rate of phenylephrine exceeds 100 mcg/min, or rate of norepinephrine exceeds 8 mcg/min, or rate of metaraminol exceeds 60mcg/min
- Subject exhibits signs and symptoms of organ failure or hypoperfusion
- Serious allergic adverse event related to midodrine
- Epinephrine requirement
- Death

If the blood pressure goal is met for more than 24 hours without IV vasopressors and the attending physician determines that the study drug is no longer required, the study drug may be discontinued at the discretion of the treating physician.

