### Adverse Event Reporting

Our patient population is by definition critically ill in the ICU. It is expected that they will have a number of unrelated adverse health events (AE) during the course of their hospital stay. Therefore, we will limit the scope of our AE monitoring and recording to the following:

- Serious Adverse Events, defined as
  - Death, believed to be related to the study drug, or a death that is unexpected considering the acuity of a patient
  - A life-threatening experience believed to be related to the study drug
  - Persistent or significant disability or incapacity that is of greater frequency or severity than what would be normally expected in the course of critical illness
  - An event that jeopardises the Human Subject and may require medical or surgical treatment to prevent one of the preceding outcomes and is not expected in the course of critical illness
- Adverse Events possibly related to the study procedures are pre-specified in the list below:
  - Hypertension
  - Bradycardia
  - Hemodynamically significant tachyarrhythmia
  - New organ failure

Evidence for adverse events related to midodrine will be assessed until completion of all study measurements. They will also be included in the FDA Annual Progress Report.

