### **POSSIBLE RISKS AND ANALYSIS OF RISK/BENEFIT RATIO**

The very common side effects of midodrine reported in previous studies include pilomotor-like reactions, paraesthesia, pruritus, and dysuria. The most common side effects are headache, supine hypertension, flushing, rash, nausea, dyspepsia, stomatitis, chills, and pain. Less common side effects comprise sleep disorders, insomnia, restlessness, excitability, irritability, and reflex bradycardia. Rare side effects are tachycardia, palpitations, abnormal hepatic function, raised liver enzymes.

These reactions rarely resulted in discontinuation of medication. These side effects may make the subject uncomfortable but do not pose any immediate harm. The subject will be assessed daily by study personnel and all efforts will be made to minimise discomfort from these side effects. Other risks that the subject may be exposed to

as a result of midodrine include hypertension, bradycardia, and tachyarrhythmias.

Patients enrolled in the study will have the same safeguards as non-study patients in an ICU setting. For patients who have stable blood pressure and adequate tissue perfusion, midodrine has been used off-label frequently to treat hypotension in our ICU. Therefore, the risks and benefits of the study drug are similar to the risks and benefits of the current standard for treating this indication in ICU patients.

Midodrine is a pregnancy category C medication. Pregnant subjects will be excluded from the study because the exposure risks of midodrine to a developing fetus are unknown. Women between the ages of 18–55, who have not had a surgical hysterectomy, will only be eligible for inclusion if they have a negative urine pregnancy test. Pregnancy testing will not need to be repeated if there is a documented negative urine pregnancy test that was obtained within 7 days prior to starting study drug, provided the woman was an ICU inpatient throughout that period of time.

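### The only drug-attributed reason to stop study drug is a serious allergic event, although the risks the protocol names for midodrine are haemodynamic

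*Combined protocol and SAP*

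**What the plan says.** The protocol, Study Procedures, sets the dosing: "Subjects will be randomised to receive either 20 mg PO every 8 hours of midodrine, or placebo PO every 8 hours". Study drug then continues until one of six events:

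- ICU discharge
- an IV vasopressor rate above the stated ceiling
- "Subject exhibits signs and symptoms of organ failure or hypoperfusion"
- "Serious allergic adverse event related to midodrine"
- a need for epinephrine
- death

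One further stop is left to the physician, under a condition: "If the blood pressure goal is met for more than 24 hours without IV vasopressors and the attending physician determines" that the drug is not needed any more.

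The Adverse Event Reporting section includes among serious events "A life-threatening experience believed to be related to the study drug", with no restriction to allergy. The same section pre-specifies hypertension, bradycardia, haemodynamically significant tachyarrhythmia and new organ failure as adverse events possibly related to study procedures. The first three are also the safety endpoints in the protocol and the SAP. The risk section says that other risks a subject may be exposed to "as a result of midodrine include hypertension, bradycardia, and tachyarrhythmias".

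**The concern.** The written safety stop does not match the written safety risks. The protocol expects a pressor drug to cause pressor and rhythm problems, and it records those problems. The one stop that depends on attribution to the drug nevertheless applies only if the event is allergic. A serious haemodynamic event that clinicians blame on study drug is reported, but no dosing instruction follows from it.

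What is at stake is patient safety on a small scale, and consistency. Blinded staff at three sites in two countries have no common instruction for this case, so the response rests on individual judgement.

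**Working it through.** No arithmetic applies. The plan states no figure on this point, and the documents give no frequency for the events concerned. The check is to take one test case through every written stop.

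**Test case (assumed for illustration).** A patient on study drug develops severe hypertension. Clinicians judge it life-threatening and related to study drug. It is a serious event under Adverse Event Reporting. There are no signs of organ failure or poor perfusion.

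| Written stop | Does it end dosing here? |
|---|---|
| ICU discharge | No; the patient is still in the ICU |
| Vasopressor rate above the ceiling | No; high pressure leads to less vasopressor, not more |
| Organ failure or hypoperfusion | No, by the terms of the case |
| Serious allergic event related to midodrine | No; the event is not allergic |
| Epinephrine requirement | No; the pressure is too high |
| Death | No |
| Physician's discretion | Only after more than 24 hours at goal off IV vasopressors, and only if the drug is judged unnecessary |

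The last row is a stop for success, not for harm. It also comes late for this problem. While an infusion is running, excess pressor effect can be countered by turning it down. Once the infusion is off, that option is gone, and the written discretion is still not available for the first 24 hours. ICU discharge may end dosing sooner.

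**The other two named risks.** A haemodynamically significant tachyarrhythmia is defined by a fall in systolic pressure of more than 20 percent. In a vasopressor-dependent patient this may well reach the hypoperfusion or ceiling stop. Bradycardia that impairs perfusion reaches the hypoperfusion stop. Severe hypertension is therefore the most plausible case left over.

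**Other places where a rule might stand.**

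- The risk section offers daily assessment by study personnel and the same safeguards as for non-study ICU patients.
- Data Monitoring has a Data Safety Monitoring Board that reviews data and adverse event reports.
- Consent provides that, when a surrogate-consented patient regains capacity and decides, "study procedures will be continued or withheld immediately".
- The SAP adds no stopping rule for individual patients.

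None of these links a drug-related event to stopping study drug.

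**Effect on the primary analysis.** The SAP analyses everyone randomised who took at least one dose. The endpoint runs from the start of study drug to the end of IV vasopressors. Neither depends on why or when dosing stopped.

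**The case against.** The strongest reply is that this is close to a drafting preference. The list is not worded as exclusive, and the Consent section already contains a stop outside it. ICU clinicians caring for a patient in danger would stop the drug. The case that slips through must be serious, drug-related and non-allergic, and it must show no organ failure, hypoperfusion, vasopressor escalation or epinephrine need. The risk section also says that the listed side effects, which include supine hypertension and reflex bradycardia, rarely led to discontinuation and pose no immediate harm. The consent form was not available for this review, so any withdrawal wording there could not be checked.

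Most of this stands, and it keeps the point small. It does not remove it. The same risk section goes on to name hypertension, bradycardia and tachyarrhythmias separately as other risks of midodrine. The general safety discretion that everyone assumes is implied, while the only discretion actually written depends on success off vasopressors. Study Procedures is the natural place for the rule, and there the word allergic narrows it.

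A reader might also infer that dosing should be held whenever heart rate falls below 50/min, because that value excludes patients at entry and the vasopressor limits at entry reappear as stops. The documents do not support that step. They give no reason for the entry cut-off. On treatment they define bradycardia differently, as a heart rate 20 percent below the primary team's goal. A fixed hold would add a second, competing definition, and it is open to clinical debate.

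**Conclusion.** The point holds as a minor one, best described as a cheap improvement. A stated rule is too narrow: followed literally, dosing goes on after a serious non-allergic drug-related event that meets no other listed stop. Severe hypertension without organ failure is the plausible example. The conclusion assumes that such an event can occur without triggering another stop. How often it would do so is unknown, so no size in patients or hours can be given.

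Two stronger readings should be avoided. A reader might infer that clinicians were barred from stopping for safety; nothing in the protocol says so, and the promise of usual ICU safeguards points the other way. A reader might also infer that the sections contradict each other or that the trial's result is at risk. They do not conflict: one section defines and reports events, the other lists stops, and the list is merely too short. The primary analysis is unaffected.

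**What to change.** In Study Procedures, replace the allergic item with: *Any serious adverse event judged related to study drug (including serious allergic reaction)*. Saying study drug rather than midodrine lets blinded clinicians apply the rule in either arm without unblinding. A pressure merely 20 percent above goal would not trigger it unless the event also met the protocol's definition of serious.

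Record the reason for each stop beside the study-drug end time already listed under Data Collection in the SAP, and report the reasons by arm. Keep these patients in the modified intention-to-treat analysis.

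The cost is one protocol amendment and one extra recorded item per stop. The downside is slightly lower drug exposure, probably more in the midodrine arm. The protocol describes enrolment as under way, so on its own terms the change could still help patients.

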### Outcomes

Study endpoints include the following:

- *Primary endpoint:*
  - Hours from initiation of midodrine until discontinuation of IV vasopressors
- *Secondary endpoints:*
  - ICU length of stay (LOS), hospital LOS, rates of ICU readmission
- *Safety endpoints:*
  - hypertension (increase in blood pressure to a systolic blood pressure (SBP) 20 percent higher than the predefined goal set by the primary team), bradycardia (decrease in heart rate 20 percent lower than the predefined goal set by the primary team), hemodynamically significant tachyarrhythmia (>20 percent decrease in systolic blood pressure).

